4.5.1 Dose Modifications

The dosage of double blind study medication may not be increased or decreased during the treatment period. Double blind study medication may be interrupted if treatment with prohibited or restricted concomitant therapies is needed. Refer to [Section 3.4.1](#).

4.6 Blinding/Unblinding

Blinding of treatment assignment is critical to the integrity of this clinical study. However, in the event of a medical emergency or pregnancy in an individual subject in which knowledge of the investigational product is critical to the subject's management, the blind for that subject may be broken by the investigator. The subject's safety takes priority over any other considerations in determining if a treatment assignment should be unblinded.

Before breaking the blind of an individual subject's treatment, the investigator should determine that the unblinded information is necessary, ie, that it will alter the subject's immediate management. In many cases, particularly when the emergency is clearly not related to the investigational product, the problem may be properly managed by assuming that the subject is receiving active product. It is highly desirable that the decision to unblind treatment assignment be discussed with the Medical Monitor, but the investigator always has ultimate authority for the decision to unblind. The Principal Investigator should only call in for emergency unblinding AFTER the decision to discontinue the subject has been made.

For this study, the method of unblinding for emergency purposes is IVRS.

For further instructions on how to unblind in the event of an emergency please consult the IVRS manual provided for this study. Following the unblinding of a subject's treatment the Investigator shall notify the Medical Monitor.

In cases of accidental unblinding, contact the Medical Monitor and ensure every attempt is made to preserve the blind.

Any request to unblind a subject for non-emergency purposes should be discussed with the Medical Monitor.

Except as noted, BMS Research and Development personnel and all vendors responsible for the conduct of the trial (protocol team) will remain blinded for the duration of the trial. Staff of BMS Research and Development that are independent from the protocol team will be unblinded to pharmacokinetic data during the course of the trial and may make recommendations to enroll additional participants to specific dosage tiers in order to obtain sufficient exposures. Any such recommendations will be considered by the Steering Committee and DMC.

The DMC will assess safety on an ongoing basis, and will have access to unblinded treatment codes. An analysis team, including a reporting statistician and programming support, who are not involved with the conduct of the study, will provide analyses to the DMC. The pharmacokineticist or designate in Clinical Pharmacology and Pharmacometrics; and programmers in Data Sciences may be unblinded in order to prepare preliminary summaries of pharmacokinetic and safety data as needed before data is more generally unblinded. This unblinded analysis team will not provide any information from unblinded analyses to the protocol team until after the trial completes.

The Bioanalytical Sciences section or its designate will be unblinded to the randomized treatment assignments in order to minimize unnecessary analysis of samples from control group subjects. Likewise, the Biotransformation section or its designate may be unblinded, if

metabolite profiling work is conducted. This unblinded analysis team will not provide any information from unblinded analyses to the protocol team until after the trial completes.

Platelet aggregation will be collected and reviewed for QC purposes by hospital and vendor personnel not associated with the clinical conduct of the study. During the double-blind treatment period, platelet aggregation will be masked to the Investigator and protocol team. One biomarker representative and/or designate, may be unmasked to review the platelet aggregation data, and will not provide any information that can potentially be unblinding to the protocol team until after the trial completes. The unmasked platelet aggregation data will be provided to the study team after the study has been completed.

4.7 Treatment Compliance

Each time study medication (BMS-986141/placebo and ASA) is dispensed, compliance will be reinforced, and subjects will be given a dosing diary to complete. When study medication is returned, compliance will be assessed based upon the subject’s interview, review of the diary and a count of the tablets returned. Compliance should be between ≥ 80 and $\leq 120\%$.

The investigator (or designee) will record the amounts of study medication dispensed and returned at each visit, as well as document reasons for non-compliance in the source document. The dates of all study medication dosing, including interruptions, missed doses or overdose, must be recorded on the eCRF. Non-compliant subjects should be re-educated regarding treatment compliance and/or the recording of dosing in the dosing diary.

4.8 Destruction or Return of Investigational Product

For this study, IP (those supplied by BMS, a vendor or sourced by the investigator) such as partially used study drug containers, vials and syringes may be destroyed on site.

If...	Then...
IP supplied by BMS (including its vendors)	Any unused IP supplied by BMS can only be destroyed after being inspected and reconciled by the responsible Study Monitor unless IP containers must be immediately destroyed as required for safety, or to meet local regulations (eg, cytotoxics or biologics). If IP will be returned, the return will be arranged by the responsible Study Monitor.
IP sourced by site, not supplied by BMS (or its vendors) (examples include IP sourced from the sites stock or commercial supply, or a specialty pharmacy)	It is the investigator’s or designee’s responsibility to dispose of all containers according to the institutional guidelines and procedures.

It is the investigator’s or designee’s responsibility to arrange for disposal, provided that procedures for proper disposal have been established according to applicable federal, state, local, and institutional guidelines and procedures, and provided that appropriate records of disposal are kept. The following minimal standards must be met:

- On-site disposal practices must not expose humans to risks from the drug

- On-site disposal practices and procedures are in agreement with applicable laws and regulations, including any special requirements for controlled or hazardous substances
- Written procedures for on-site disposal are available and followed. The procedures must be filed with the site's SOPs and a copy provided to BMS upon request
- Records are maintained that allow for traceability of each container, including the date disposed of, quantity disposed, and identification of the person disposing the containers. The method of disposal, ie, incinerator, licensed sanitary landfill, or licensed waste disposal vendor must be documented
- Accountability and disposal records are complete, up-to-date, and available for the Monitor to review throughout the clinical trial period

It is the investigator's or designee's responsibility to arrange for disposal of all empty containers.

If conditions for destruction cannot be met the responsible Study Monitor will make arrangements for return of IP provided by BMS (or its vendors). Destruction of non-IP sourced by the site, not supplied by BMS, is solely the responsibility of the investigator or designee.

Please refer to [Section 9.2.2](#) for additional guidance on IP records and documentation.

4.9 Retained Samples for Bioavailability / Bioequivalence

Not Applicable.

5 STUDY ASSESSMENTS AND PROCEDURES

5.1 Flow Chart/Time and Events Schedule

Table 5.1-1: Screening Procedural Outline (CV006004)

Procedure	Screening (Visit 1)	Notes
Eligibility Assessments		
Informed Consent	X	
Inclusion/Exclusion Criteria	X	
NIH Stroke Scale (NIHSS)	X	For anyone presenting with acute neurological deficit
ABCD2	X	For TIAs only
Ischemic Stroke Sub-typing (Oxfordshire (OCSP) classification)	X	For strokes only
Medical History	X	
Safety Assessments		
Physical Examination	X	
Physical Measurements	X	Height, Weight
Vital Signs	X	To be done prior to blood draws and ECG.
Electrocardiogram (ECG)	X	12 lead
Concomitant Medications	X	
Assessment for Serious Adverse Events	X	All SAEs must be collected from the date of subject's written consent until 30 days post discontinuation of dosing or subject's participation in the study, if the last scheduled visit occurs at a later time.
Local Laboratory Tests		Screening laboratory tests to be analyzed at a local lab. Retesting should be done locally during screening.
Plasma aPTT, INR and PT	X	

Table 5.1-1: Screening Procedural Outline (CV006004)

Procedure	Screening (Visit 1)	Notes
Pregnancy test (serum or urine) WOCBP only	X	Pregnancy test to be done locally at screening. All WOCBP must have a negative pregnancy test within 24 hours prior to dosing.
Follicle stimulating hormone (FSH) Test	X	Post-menopausal women under age 55 only. See Appendix 1 .
Clinical Chemistry	X	
Hematology	X	
Urinalysis	X	
MRI	X	At Screening or No later than 24 hours after randomization

Table 5.1-2: Part 1 Procedural Outline (CV006004)

Procedure	Day 1 (Visit 2)	Day of Hospital Discharge ^a (Visit 3)	Day 10 Telephone Contact ^b (Visit 4)	Day 28 (EOT) / Early D/C ^{a,b} (Visit 5)	Follow-up Day 90 ^{a,b} (Visit 6)	Notes
Safety Assessments						
Physical Examination		X		X		
Physical Measurements		X		X		Weight
Vital Signs		X		X		To be done prior to blood draws and ECG.
Electrocardiogram (ECG)				X		12-lead
Concomitant Medications	X	X	X	X	X	
Assessment of Non-Serious Adverse Events	X	X	X	X	X	
Assessment for Serious Adverse Events	X	X	X	X	X	All SAEs must be collected from the date of subject's written consent until 30 days after discontinuation of dosing or subject's participation in the study, if the last scheduled visit occurs at a later time.
Central Laboratory						Chemistry and hematology samples for Day 1 pre-dose labs and those drawn throughout the study to be analyzed by the central laboratory. Urinalysis testing (refer to Table 5.3.7-1) will be done locally for all time points.
Pregnancy test (serum or urine) WOCBP only	X			X		To be done locally. All WOCBP must have a negative pregnancy test within 24 hours prior to dosing.
Clinical Chemistry	X	X ^c		X		
Hematology	X	X ^c		X		

Table 5.1-2: Part 1 Procedural Outline (CV006004)

Procedure	Day 1 (Visit 2)	Day of Hospital Discharge ^a (Visit 3)	Day 10 Telephone Contact ^b (Visit 4)	Day 28 (EOT) / Early D/C ^{a,b} (Visit 5)	Follow-up Day 90 ^{a,b} (Visit 6)	Notes
Urinalysis	X	X		X		To be analyzed locally at all time points
MRI	X*			X**		*No later than 24 hours after randomization if not done prior to randomization ** +/- 3 days from Day 28 For subjects that stop treatment early the MRI should be done on Day 28
Pharmacokinetic (PK)						
Serial/Sparse Blood PK Sampling	X			X		On Day 1, the last PK sample is collected 24 hrs (+/- 11 hrs) after first dose of study medication and before Day 2 dose
Biomarker Assessments						
Platelet Aggregation	X			X		To be performed at select sites. Samples should be collected at the same time as the time-matched PK samples. Day 1-24 hr sample to be collected 24 hrs (+/- 11 hrs) after first dose of study medication and before Day 2 dose.
Exploratory Biomarker Assessments						
[REDACTED]	■			■		[REDACTED]
[REDACTED]	■			■		[REDACTED]

Table 5.1-2: Part 1 Procedural Outline (CV006004)

Procedure	Day 1 (Visit 2)	Day of Hospital Discharge ^a (Visit 3)	Day 10 Telephone Contact ^b (Visit 4)	Day 28 (EOT) / Early D/C ^{a,b} (Visit 5)	Follow-up Day 90 ^{a,b} (Visit 6)	Notes
						
Clinical Drug Supplies						
Randomize	X					
Review study drug administration compliance (BMS- 986141 or matching placebo with ASA)		X	X	X		Subjects MUST be instructed to stop study medication dosing on Day 28, even if visit will not occur on Day 28. Telephone contact with subject to review medication compliance and assess subject's health status
Dispense Study Drug	X					

^a Subjects should participate in all study visits even if study medication dosing has been discontinued.

^b Visit window is +/- 3 days.

^c Laboratory tests may be done on the day prior to discharge.

Table 5.1-3: Part 2 Procedural Outline (CV006004)

Procedure	Day 1 (Visit 2)	Day of Hospital Discharge ^a (Visit 3)	Day 10 Telephone Contact ^b (Visit 4)	Day 28 ^{a,b} (Visit 5)	Day 56 ^{a,b} (Visit 6)	Day 90 (EOT) / Early D/C ^{a,b} (Visit 7)	Follow-up Day 120 ^{a,b} (Visit 8)	Notes
Safety Assessments								
Physical Examination		X		X				
Physical Measurements		X		X	X	X		Weight
Vital Signs		X		X	X	X		To be done prior to blood draws and ECG.
Electrocardiogram (ECG)				X		X		12-lead
Concomitant Medications	X	X	X	X	X	X	X	
Assessment of Non-Serious Adverse Events	X	X	X	X	X	X	X	
Assessment of Serious Adverse Events	X	X	X	X	X	X	X	All SAEs must be collected from the date of subject's written consent until 30 days post discontinuation of dosing or subject's participation in the study, if the last scheduled visit occurs at a later time.
Central Laboratory								
Chemistry and hematology samples for Day 1 pre-dose labs and those drawn throughout the study to be analyzed by the central laboratory. Urinalysis testing (refer to Table 5.3.7-1) will be done locally for all time points.								
Pregnancy test (serum or urine) WOCBP only	X			X	X	X [†] X		To be performed locally. All WOCBP must have a negative pregnancy test within 24 hours prior to dosing.

Table 5.1-3: Part 2 Procedural Outline (CV006004)

Procedure	Day 1 (Visit 2)	Day of Hospital Discharge ^a (Visit 3)	Day 10 Telephone Contact ^b (Visit 4)	Day 28 ^{a,b} (Visit 5)	Day 56 ^{a,b} (Visit 6)	Day 90 (EOT) / Early D/C ^{a,b} (Visit 7)	Follow-up Day 120 ^{a,b} (Visit 8)	Notes
								† Home pregnancy test kit to be sent home with WOCBP subjects to perform pregnancy test on Day 84. Test result to be recorded in patient diary. Pregnancy test must also be performed at the Day 90 visit.
Clinical Chemistry	X	X ^c		X	X	X		
Hematology	X	X ^c		X	X	X		
Urinalysis	X	X		X	X	X		To be analyzed locally at all time points
MRI	X*			X**				*No later than 24 hours after randomization if not done prior to randomization ** +/- 3 days from Day 28 For subjects that stop treatment early the MRI should be done on Day 28
Pharmacokinetic (PK)								
Serial/Sparse Blood PK Sampling	X			X				On Day 1, the last PK sample is collected 24 hrs (+/- 11 hrs) after first dose of study medication and before Day 2 dose.

Table 5.1-3: Part 2 Procedural Outline (CV006004)

Procedure	Day 1 (Visit 2)	Day of Hospital Discharge ^a (Visit 3)	Day 10 Telephone Contact ^b (Visit 4)	Day 28 ^{a,b} (Visit 5)	Day 56 ^{a,b} (Visit 6)	Day 90 (EOT) / Early D/C ^{a,b} (Visit 7)	Follow-up Day 120 ^{a,b} (Visit 8)	Notes
Biomarker Assessments:								
Platelet Aggregation	X			X				To be performed at select sites. Samples should be collected at the same time as the time-matched PK samples. Day 1-24 hr sample to be collected 24 hrs (+/- 11 hrs) after first dose of study medication and before Day 2 dose.
Exploratory Biomarker Assessments								
[REDACTED]	■			■				[REDACTED]
[REDACTED]	■			■	■	■		[REDACTED]

Table 5.1-3: Part 2 Procedural Outline (CV006004)

Procedure	Day 1 (Visit 2)	Day of Hospital Discharge ^a (Visit 3)	Day 10 Telephone Contact ^b (Visit 4)	Day 28 ^{a,b} (Visit 5)	Day 56 ^{a,b} (Visit 6)	Day 90 (EOT) / Early D/C ^{a,b} (Visit 7)	Follow-up Day 120 ^{a,b} (Visit 8)	Notes
								
Clinical Drug Supplies								
Randomize	X							
Review study drug administration compliance (BMS- 986141 or matching placebo with ASA)		X	X	X	X	X		Telephone contact with subject to review medication compliance and assess subject's health status
Dispense Study Drug	X			X	X			

^a Subject should participate in all study visits even if study medication has been discontinued.

^b Visit window is +/- 3 days.

^c Laboratory tests may be done on the day prior to discharge.

5.1.1 Retesting During Screening or Lead-in Period

Retesting of laboratory parameters and/or other assessments within any single Screening or Lead-in period will be permitted (in addition to any parameters that require a confirmatory value).

Any new result will override the previous result (ie, the most current result prior to Randomization) and is the value by which study inclusion will be assessed, as it represents the subject's most current, clinical state.

Laboratory parameters and/or assessments that are included in [Table 5.1-1](#), Screening Procedural Outline may be repeated in an effort to find all possible well-qualified subjects. Consultation with the Medical Monitor may be needed to identify whether repeat testing of any particular parameter is clinically relevant.

5.2 Study Materials

BMS will supply the study sites with the following:

- Patient Dosing Diaries to be completed daily after hospital discharge to record study medication taken. Diaries should be completed by all randomized subjects and reviewed for accuracy and completeness by the study staff at each study visit (refer to [Section 4.7](#)). WOCBP to record Day 84 urine pregnancy test result in diary.
- Patient Emergency Card
- Protocol specified rating scales
- Electronic case report forms

The Imaging Core Lab will supply the following:

- Image acquisition guidelines and submission processes will be outlined in the CV006004 Imaging Manual, to be provided by the imaging core lab.

5.3 Safety Assessments

Only data for the procedures and assessments specified in the protocol should be submitted to BMS on a case report form. Additional procedures and assessments may be performed as part of the subject's standard of care; however, data for these assessments should remain in the subject's medical record and should not be provided to BMS, unless needed to support an AE, SAE report, adjudication dossier or specifically requested by the sponsor.

5.3.1 Imaging Assessment for the Study

Any incidental findings of potential clinical relevance that are not directly associated with the objectives of the protocol should be evaluated and handled by the Study Investigator as per standard medical/clinical judgment.

Imaging is an important component of the study. All subjects will undergo standardized MRI at baseline and at the Day 28 visit. Images may be evaluated locally, but must also be submitted for

analysis by the Imaging Adjudication Committee. Results of centralized analysis will not be returned to the sites.

In addition, various types of imaging may be used for the clinical evaluation of suspected efficacy or safety endpoints. For these events, investigators should perform and analyze imaging and other assessments according to their normal clinical practice and the local standard of care, and base any treatment decisions on the local interpretation. Results of these assessments will also be submitted for adjudication by the CEC. Results of the adjudication by the CEC will not be returned to the sites.

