3.3.1 Inclusion Criteria

1. Signed Written Informed Consent

- a) Subjects or Legally Acceptable Representatives (LAR), must be willing and able to give signed and dated written informed consent. (Note: Consent by a LAR will only be allowed if permitted by local regulations.)

2. Target Population

- a) Either acute ischemic stroke or high-risk TIA as defined here
 - i) Acute ischemic stroke, defined as:
 - (1) Neurological deficit attributed to the focal brain ischemia, and either of the following:
 - Persistent signs or symptoms of the ischemic event at the time of randomization
 - Acute, ischemic brain lesion documented by computed tomography (CT) scan or MRI

AND

(2) National Institutes of Health Stroke Score (NIHSS) ≤ 7

ii) High-risk TIA, defined as:

(1) Neurological deficit of acute onset attributed to focal ischemia of the brain by history or examination with complete resolution of the deficit, and at least one of the following:

- ABCD2 score ≥ 4 OR motor or speech symptoms
- Symptomatic intracranial arterial occlusive disease documented by transcranial Doppler, ultrasound or vascular imaging, defined as at least 50% narrowing in diameter of a vessel that could account for the clinical presentation
- Documented internal carotid arterial occlusive disease, defined as at least 50% narrowing in diameter of a vessel that is presumed to be atherosclerotic and could account for the clinical presentation
- Documented stenosis in the vertebral circulation that is presumed to be atherosclerotic and could account for the clinical presentation

- b) CT or MRI ruling out hemorrhage or other pathology, such as vascular malformation, tumor, or abscess that could explain symptoms or contraindicate therapy
- c) Randomization occurring within 48 hours after onset of symptoms; if the time of onset of symptoms is unknown, such as when symptoms are first present on awakening, onset should be considered as time last seen normal
- d) Subject is able to be evaluated by study-specific MRI no later than 24 hours after randomization, does not have contraindications to the performance of the MRI, and has suitable weight and circumference. See [Section 3.4.3](#) for further details.
- e) Ability to tolerate ASA at a dose from 75 to 162 mg/day
- f) Subject Re-enrollment: This study does not permit the re-enrollment of a subject that has discontinued the study as a pre-treatment failure

3. Age and Reproductive Status

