3.3.2 Exclusion Criteria

1. Target Disease Exceptions

- a) Any history of atrial fibrillation (AF) other than transient AF related to cardiac surgery
- b) Severe left ventricular systolic dysfunction, left ventricular thrombus, or other high-risk cardioembolic source deemed the likely cause of brain ischemia
- c) TIA symptoms limited to isolated numbness, isolated visual changes, or isolated dizziness/vertigo
- d) Carotid or vertebral stenosis for which there is a plan for revascularization therapy
- e) Any condition requiring ongoing treatment with an anticoagulant after discharge. For prophylactic measures to prevent deep vein thrombosis (DVT), pneumatic pressure devices are preferred

2. Medical History and Concurrent Diseases

- a) Subjects with known bleeding diathesis or coagulation disorder (eg, thrombotic thrombocytopenic purpura)
- b) History of previous non-traumatic or traumatic intracranial hemorrhage at any time
- c) Acute gastrointestinal ulcer or history of gastrointestinal (GI) bleed which required medical treatment within the past 3 months

- d) Planned or anticipated invasive surgery or procedure during study duration
- e) Persistent, uncontrolled hypertension (systolic BP > 180 mm Hg, or diastolic BP > 100 mm Hg) that does not respond to acute treatment
- f) Moderate or severe hepatic impairment, defined as Child-Pugh Class B or C; (see [Appendix 5](#))
- g) Moderate to severe renal impairment, defined as estimated glomerular filtration rate (eGFR) < 45 mL/min; (see [Section 5.3.7.1](#))
- h) Any other reason, in the opinion of the investigator that the subject may be at undue risk from study participation
- i) Qualifying ischemic event induced by angiography or surgery
- j) Any gastrointestinal surgery that could impact upon the absorption of study drug
- k) Inability to tolerate oral medication or swallow tablets whole
- l) Inability to undergo venipuncture and/or tolerate venous access
- m) Subjects in whom MRI procedures cannot be performed. [Section 3.4.3](#) provides a list of some common conditions that may preclude the subjects from having MRI. However, this should not be used as a substitute for local clinical standards of care. The ultimate decision to perform any of these procedures in an individual subject in this study rests with the site radiologist, the investigator and the standard set by the local ethics committee/institutional review board

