3.5 Discontinuation of Subjects following any Treatment with Study Drug

During treatment period circumstances may arise which require temporary or permanent discontinuation of investigational product. For guidance related to the temporary discontinuation please refer to [Section 3.4.1](#).

Subjects MUST discontinue investigational product (and non-investigational product at the discretion of the investigator) for any of the following reasons:

- Subject's request to stop study treatment
- Any clinical adverse event (AE), laboratory abnormality or intercurrent illness which, in the opinion of the investigator, indicates that continued participation in the study is not in the best interest of the subject
- Any clinical condition requiring treatment with a prohibited medication for more than 14 days
- Termination of the study by Bristol-Myers Squibb (BMS)
- Loss of ability to freely provide consent through imprisonment or involuntarily incarceration for treatment of either a psychiatric or physical (eg, infectious disease) illness
- Severe non-compliance to protocol, as judged by the investigator and/or Sponsor (BMS)
- Incorrect enrollment (ie, the subject does not meet the required inclusion/exclusion criteria) for the study, as determined after consultation with the sponsor
- Pregnancy
- Moderate or severe renal impairment defined as eGFR < 45 mL/min (see [section 5.3.7.1](#)) for more than 7 days.
- Subjects with an ALT and/or AST > 3× ULN will be scheduled for a follow up visit within 3 days following the receipt of the result. Subjects should be discontinued from study if the initial and repeat laboratory tests meet any of the following criteria:
 - ◆ ALT and/or AST are > 3× ULN and total bilirubin (TB) > 2× ULN

- ◆ ALT and/or AST are $> 5 \times$ ULN for ≥ 14 consecutive days, at any time after initial confirmatory results
- ◆ ALT and/or AST are $\geq 10 \times$ ULN
- Subjects requiring treatment with strong CYP3A4 inhibitors or strong CYP3A4 inducers
- Subjects treated with any intravenous or intra-arterial thrombolysis or with mechanical thrombectomy

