7.2.2 Relevant Protocol Deviations

Relevant deviations from the study protocol will be documented and accounted for in presenting the data summaries, listings and descriptive statistical analyses. Any changes from planned protocol-specified analyses will be defined in the SAP and reported in the CSR. The relevant protocol deviations are described in the table below.

Table 7.2.2-1: List of Relevant Protocol Deviations

Number	RPD Criteria
1	Subject randomized but not dosed
2	Error in treatment assignment (resulting in a subject receiving a treatment other than that assigned by the IVRS) during the first 28-day interval
3	Poor treatment compliance for either BMS-986141 or ASA (compliance less than 80% or more than 120%) during first 28-day interval
4	Randomized subjects with history of atrial fibrillation (AF) other than transient AF related to cardiac surgery at enrollment (per Exclusion Criteria 1a from the protocol)
5	Randomized subjects with unrecognized or misdiagnosed intracranial hemorrhage (ICH) as determined by the central reader based on the baseline study specific MRI (presence of type 1 or 2 parenchymal hematoma)
6	Randomized subjects who took no dose of ASA or dose of ASA not within limits designated by the protocol for ≥ 5 consecutive days in the first 28 days of the treatment period
7	Randomized subjects who took oral anticoagulants or prohibited antiplatelet therapy, other than study medication, for > 2 consecutive days during the first 28days of the treatment period
8	Randomized subjects that were treated with a strong CYP3A4 inhibitor for > 5 days during the first 28 days of the treatment period ^a

a: CYP3A4 inhibitors will be defined in a separate file maintained by the study team and will be classified as weak, moderate, or strong.

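### A hematoma that only the central reader sees on the baseline MRI has no stated route back to the investigator

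*Protocol*

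**What the plan says.** SAP 7.2.2, Table 7.2.2-1 item 5, lists as a relevant protocol deviation "Randomized subjects with unrecognized or misdiagnosed intracranial hemorrhage (ICH) as determined by the central reader based on the baseline study specific MRI", and specifies type 1 or 2 parenchymal hematoma.

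Protocol 5.3.1 covers the study MRIs at baseline and Day 28. On who reads them it says "Images may be evaluated locally, but must also be submitted for" analysis by the Imaging Adjudication Committee (IAC). It then says "Results of centralized analysis will not be returned to the sites". The same section says that incidental findings of possible clinical relevance, if not directly tied to the protocol objectives, "should be evaluated and handled by the Study Investigator as per standard medical/clinical judgment".

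For eligibility, Protocol 3.3.1 inclusion 2b asks for "CT or MRI ruling out hemorrhage or other pathology" that could explain symptoms or contraindicate therapy. Protocol 3.3.2 exclusion 2b is "History of previous non-traumatic or traumatic intracranial hemorrhage at any time".

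Protocol 3.5 begins its list of stopping reasons with "Subjects MUST discontinue investigational product". One reason is "Incorrect enrollment (ie, the subject does not meet the required inclusion/exclusion criteria) for the study, as determined after consultation with the sponsor". Another is any clinical event or intercurrent illness that, in the investigator's opinion, makes continuing against the subject's interest.

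**The concern.** The SAP recognizes that a central reader may see a hematoma that entry imaging missed, and it uses that finding only to classify data. The protocol says without qualification that central results do not go back to the site, and it does not require the site to read the scan itself. Taken together, the one party certain to look at the image is the one whose finding is withheld from the person responsible for the subject.

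What is at stake is patient safety: continued antithrombotic study drug on top of ASA in someone with an intracranial hematoma that is on record but not communicated.

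**Working it through.** No arithmetic underlies the point itself. The check is whether the documents, read together, contain a path from the central finding to the investigator.

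1. **Can the subject already be on drug when the scan is done or read?** Yes. Protocol 3.1 and Table 5.1-2 allow the baseline MRI up to 24 hours after randomization. Protocol 3.1 says imaging should not hold up randomization and wants the first dose given promptly once the subject is randomized. Dosing is not made conditional on the study MRI or on its central read.

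2. **Would the site see the hematoma independently?** Perhaps. Local evaluation of the study MRI is permitted, not required. By contrast, for imaging of suspected efficacy or safety events, 5.3.1 tells investigators to analyze the images and to base treatment on their local interpretation. The study MRI carries no such instruction.

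3. **Does the incidental-findings sentence supply a path?** No. It tells the investigator to handle findings, but it does not bring a central finding to the site. It is also limited to findings not directly tied to the objectives, and bleeding is a safety objective (Protocol 1.3.3).

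4. **Is there an exception elsewhere?** None appears in Protocol 3.5, 5.4.2, 7.1 or 7.2. The Data Monitoring Committee reviews reports of bleeding (7.1), but a silent hematoma unknown to the site gives the site nothing to report. Mandatory submission to the clinical events committee is for clinically overt bleeding (5.3.2).

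5. **What would follow if the investigator knew?** A hemorrhage present at entry bears on inclusion 2b and possibly on exclusion 2b. It would therefore prompt the incorrect-enrollment question in 3.5, to be settled with the sponsor, or the investigator-judgment reason in the same list. Neither review can start at the site without the finding.

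6. **Who would gain from being told?** The time of the baseline central read is not stated. Protocol 5.4.2 describes review of the baseline and Day 28 scans for new infarction, which is compatible with reading both after Day 28.
   - Part 1: study drug stops on Day 28 (Protocol 4.5), so notice after that cannot change study-drug exposure.
   - Part 2: dosing runs to Day 90, so even a read on Day 28 would leave up to 90 − 28 = 62 planned dosing days.
   - SAP 2.2 says no Phase B subject will be in Part 1. If the 8 mg arm opens and the targets in Protocol Table 8.1-1 hold, Phase B is 4 × 270 = 1080 of 1312 subjects (1080/1312 = 82%). Most subjects would then be in Part 2.

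7. **Does any analysis depend on this?** Deviation 5 enters only through the All Evaluable Subjects population (SAP 6.3), which is used in one sensitivity analysis of the primary endpoint (SAP 7.5.1.1). The primary analysis is on all randomized subjects and the safety analyses are on all treated subjects. Neither set excludes anyone for deviation 5.

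**The case against.** The strongest reply is that the governing documents are not in front of us. Protocol 7.2 leaves the full role of the IAC to its charter, and 5.4.2 and 5.2 point to an Imaging Charter and imaging manuals. Any of these could hold an alert rule. The no-return sentence can also be read narrowly: it follows directly on submission to the IAC, whose task in 5.4.2 and 7.2 is to detect infarction, and SAP item 5 says central reader without naming the IAC. On that reading only endpoint reads are withheld.

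This stands in part. An alert rule may exist. But the sentence in 5.3.1 refers to centralized analysis in general and has no qualifier, so such a rule would conflict with the protocol as written. At the least, 5.3.1 needs a cross-reference.

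Other parts of the reply limit what a reader may infer:

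- **That the sponsor expects these cases.** Listing a deviation category provides for it and does not predict it. Inclusion 2b, optional local reading and investigator handling of incidental findings leave a small residual group.
- **That study drug must stop automatically.** A subject whose entry CT or MRI ruled out hemorrhage arguably met inclusion 2b, exclusion 2b speaks of history, and 3.5 requires consultation with the sponsor. What is lost is the review, not a certain stop.
- **That the plan forbids anyone to act.** Nothing bars the sponsor from acting on the finding. The documents just do not require that the investigator be told.
- **That notification would prevent early exposure.** With the read time unstated, it might not.

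**Conclusion.** The concern holds as a gap in safety communication. The SAP provides for a central finding of hematoma at baseline, and the protocol, followed as written, does not require that finding to reach the investigator. A subject could therefore stay on blinded study drug plus ASA without review under Protocol 3.5.

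Its size cannot be given as a number. The documents state no rate of missed hemorrhage, no share of baseline scans taken after the first dose and no central read time. The event should be uncommon, and its possible consequence is serious for the subject concerned. The benefit of a change is clearest in Part 2.

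A reader might also infer that the trial's results are compromised. The documents do not support that, since no alpha, power, primary-endpoint or bleeding-count rule depends on the point.

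The conclusion assumes that the central reader in SAP item 5 falls under the centralized analysis of 5.3.1, and that no charter alert rule already governs.

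**What to change.** Add one exception to Protocol 5.3.1: an intracranial hemorrhage seen centrally on a study MRI is notified to the investigator and the medical monitor when it is detected, for review under Section 3.5. Infarct reads remain unreturned. If the imaging or IAC charter already has an alert rule, cite it in 5.3.1 so that the two texts agree.

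The cost is a protocol amendment, with ethics approval and, where applicable, health-authority approval (Protocol 9.1.1), and a small notification workflow. The existing central read triggers the notice, so no extra scan, reader or real-time reading service is needed. Telling the site of a hemorrhage does not disclose treatment assignment.
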